Official Title of the study:

“Study of an Intraoperative Frontal
Electroencephalographic Marker of Preoperative
Frailty in Patients Over 65 Years of Age for Elective
Non-cardiac Surgery.”

NCT number: NCT04783662

Date of the document: January 14th, 2021

Statistical Plan: Intraoperative EEG Marker of Preoperative Frailty in Elderly Patients

We will study the correlation between alpha (8-12Hz) spectral power and total spectral power (0.5-30 Hz) with the different frailty scales (Fried, FRAIL, CFS) using Spearman correlation. Then, we will use an empirical bootstrap for statistical inferences for EEG analysis. First, we will bootstrap for window estimates that do not overlap. Next, we will compute the median of the bootstrap estimates at the subject level, and then compute the group median of this estimate. We will calculate the median difference between the groups and then iterate the above procedure 5,000 times to obtain a distribution of the median difference between the groups. We will calculate the 99% confidence interval of this distribution. Our threshold of statistical significance will be defined when the upper and lower confidence intervals of the mean difference distribution do not border zero in a contiguous frequency range greater than 2 bandwidths (2 W). As a sensitivity analysis, we will re-analyze our results after performing a matching by age and a previous cognitive evaluation. For descriptive statistics, continuous data will be presented using the mean \pm standard deviation or the median and its interquartile range, as appropriate. In addition, the groups will be compared using Student's t test for independent samples or Mann-Whitney U test according to their distribution. In the case of categorical data, they will be presented as absolute counts and their corresponding percentage. Differences between groups will be studied using Fisher's test or Chi square. For the association study, univariate and multivariate linear or logistic regressions will be performed, as appropriate. A significance level of 0.05 with its respective 95% confidence interval will be considered.

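### The EEG bootstrap as written resamples windows but not patients, so its 99% interval omits between-patient variation and can flag null group differences far more often than 1%

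*SAP*

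**What the plan says.** The SAP is one paragraph, and it sets out the EEG comparison as an ordered recipe:

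1. Draw: "we will bootstrap for window estimates that do not overlap".
2. Summarise: "compute the median of the bootstrap estimates at the subject level, and then compute the group median of this estimate".
3. Take the difference between groups and repeat: "iterate the above procedure 5,000 times to obtain a distribution of the median difference between the groups".
4. Interval: "We will calculate the 99% confidence interval of this distribution".
5. Decide: a difference counts as significant when the interval stays clear of zero over an unbroken frequency range wider than 2W. The SAP calls this its threshold of statistical significance.

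Windows are the only unit drawn. Patients appear only in step 2, as units to be summarised, and no other sentence adds a draw of patients. The method is introduced with the words "we will use an empirical bootstrap for statistical inferences for EEG analysis"; the type of interval (percentile or basic, that is, reflected) is not named.

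**The concern.** A comparison of groups is a statement about patients, so its uncertainty must include how the difference would change with other patients. If the same patients enter all 5,000 iterations, the spread of the differences comes only from window-to-window noise within each patient. Two consequences follow.

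- The interval is too narrow whenever patients differ in EEG power. The SAP itself expects them to differ, since it correlates power "with the different frailty scales (Fried, FRAIL, CFS) using Spearman correlation".
- The interval shrinks as recordings lengthen, even if no patient is added.

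At stake is the plan's stated significance rule for EEG differences between groups, and the error runs towards false positives. The matched sensitivity analysis does not help as far as the text shows, because no patient draw is stated there either.

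**Working it through.** **Inputs.** From the SAP: window-only draw, patient median, group median, difference, 99% interval (nominal two-sided error 1% at one frequency). The SAP gives no group sizes, window counts or variances, so these are assumptions: 15 or 40 patients per group; K = 30, 60 or 150 independent windows per patient; normal patient effects with SD r and normal window noise with SD 1. There is no true group difference.

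**Large-sample check.** The sampling variance of one patient's median is v = (π/2)/K. Observed patient medians have variance r² + v, and a window redraw adds v again. The share of the true variance of the group median that window redraws reproduce is

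S = (2/π) · arccos(ρ) · (r² + 2v)/(r² + v), with ρ = (r² + v)/(r² + 2v),

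and the error at one frequency is about 2[1 − Φ(2.576·√S)].

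With K = 60 and r = 0.5:
- v = 1.571/60 = 0.0262.
- ρ = 0.2762/0.3024 = 0.913, and arccos(ρ) = 0.419.
- S = 0.637 × 0.419 × 1.095 = 0.292.
- 2.576 × √0.292 = 1.39, so the error is about 16.4%.

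The same steps give S = 1.04, 0.568 and 0.146 at r = 0.1, 0.25 and 1, hence errors of about 0.8%, 5.2% and 32.5%.

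**Simulation, 99% percentile interval, 15 per group, 60 windows** (1,000 trials per r, 800 resamples; Monte Carlo SE at most 1.6 points):

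| r | As written | Patients also drawn | Width ratio (patients drawn / as written) |
|---|---|---|---|
| 0.1 | 0.0% | 0.0% | 1.29 |
| 0.25 | 4.5% | 0.2% | 1.55 |
| 0.5 | 16.4% | 0.4% | 2.06 |
| 1 | 34.3% | 0.9% | 3.12 |
| 1.5 | 49.8% | 0.8% | 4.14 |

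**More patients.** With 40 per group (500 trials), the as-written error at r = 0.1, 0.25, 0.5 and 1 is 0.8%, 3.0%, 14.2% and 39.8%, against 0.2%, 0.0%, 0.2% and 1.0% with patients drawn.

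**Longer recordings, r = 1, 15 per group.** With 30, 60 and 150 windows the as-written error is 24.5%, 34.3% and 53.0%. The width falls from 0.98 to 0.78 to 0.56 window SDs. With patients drawn the width stays at about 2.4 to 2.5.

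**Separate simulation.** With 20 per group and 21 windows (500 trials), the as-written error is 6.0% at r = 0.5 and 22.4% at r = 1, against 0.2% and 0.6% with patients drawn.

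**Interval type, 15 per group, 60 windows.** The basic form has higher error. For r from 0.25 to 1.5 it gave 15.6% to 54.9% as written, and still 5.0% to 7.4% with patients drawn.

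**The 2W rule (rough).** This used 15 per group, 60 windows and 0.5–30 Hz in 0.5 Hz steps, with assumed correlation lengths of 3 Hz (patients) and 1 Hz (windows), 2W taken as 1–4 Hz, 120 trials and 200 resamples. The chance of at least one falsely flagged band was:

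| r | As written | Patients also drawn |
|---|---|---|
| 0.1 | 0% | 0% |
| 0.25 | 3–26% | 0–1% |
| 0.5 | 22–81% | 0–3% |
| 1 | 67–99% | 2–12.5% |

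A second setting (20 per group, 21 windows, 30 bins, a run of at least 3 bins, 40 trials) gave 0%, 12.5% and 57.5% at r = 0.25, 0.5 and 1 as written, and no false flags with patients drawn.

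**The case against.** - **The text does not say that patients are held fixed.** It is a short summary, and the authors may intend a patient draw. That may be so. But the steps are ordered and explicit, and an analyst who follows them would not code such a draw. The point concerns the wording, not what will in the end be run.
- **The size is unknown.** This stands. No single error rate can be assigned to this trial, and at r = 0.1 with 60 windows the percentile interval does no harm.
- **The 2W rule guards against chance findings.** It does so for isolated bins. A chance imbalance of patients can move neighbouring frequencies together, so a wide run is weak protection.
- **The band-level figures are imprecise.** This stands. With 200 resamples a 99% limit rests on the one or two most extreme draws. A small rerun with 800 resamples lowered the as-written rate at r = 0.25 from 9.5% to 4.8% (2W = 2 Hz) and left it at 52% at r = 0.5. The band figures show direction only; the single-frequency result does not depend on them.
- **The interval type is not really open.** An interval of the distribution of differences reads most naturally as its percentiles. This is fair: naming the form is a clarification, not a second error.
- **Other analyses are sound.** The Spearman correlations, the t or Mann-Whitney comparisons and the regressions do not use this interval. They do not repair the frequency-by-frequency group claim.

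**Conclusion.** The concern holds. As written, the interval behind the EEG significance rule carries window noise only, and its 99% level is not met once patients differ appreciably. At 60 windows, error above nominal is visible from about r = 0.25. At r = 1 it is roughly a third with 15 per group and 40% with 40 per group, against a nominal 1%. The rates rest on assumed group sizes, window counts, r, normality and independent windows. The direction follows from the procedure itself. The wording should be corrected before the EEG comparison is run.

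**What to change.** Replace the bootstrap sentences with wording such as:

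> In each of 5,000 iterations we (1) draw patients with replacement within each group, to that group's size; (2) within each drawn patient, draw that patient's non-overlapping windows with replacement; (3) take the patient median, the group median and the difference between groups. The 99% interval is the percentile interval (0.5th to 99.5th percentile of the 5,000 differences).

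The 2W rule can stay. Its sentence refers to a mean-difference distribution although the procedure builds median differences; this clerical mismatch should be aligned at the same time.

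The cost is two sentences of text and one extra resampling step in code, with no new data. Intervals widen by about 1.3 times at r = 0.1 and 3 to 4 times at r = 1 to 1.5 (60 windows), so power falls. At small r the corrected interval is conservative (0.0% to 0.2% error against 1%). A pointwise 99% interval with the 2W rule still does not fix the band-level error at 1%.

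Permuting group labels across patients would also be a valid test, but it yields a null distribution and not an interval, so the decision rule would have to be reworded.

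### Does the EEG significance rule test a mean difference that the bootstrap never produces?

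*SAP*

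**What the plan says.** The SAP consists of one paragraph under the heading Statistical Plan: Intraoperative EEG Marker of Preoperative Frailty in Elderly Patients. For the EEG spectra it describes a bootstrap over non-overlapping windows. From the resampled windows the analyst is to "compute the median of the bootstrap estimates at the subject level, and then compute the group median of this estimate". The between-group step follows: "We will calculate the median difference between the groups and then iterate the above procedure 5,000 times". The purpose of the iteration is to "obtain a distribution of the median difference between the groups", and then: "We will calculate the 99% confidence interval of this distribution".

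The sentence after that sets the threshold. A difference counts as significant when "the upper and lower confidence intervals of the mean difference distribution do not border zero" across a contiguous band of frequencies wider than two bandwidths.

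Elsewhere in the paragraph, means appear only in the descriptive part: mean and standard deviation, or median and interquartile range, with Student's t test or the Mann-Whitney test to match.

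**The concern.** The statistic changes between two adjacent sentences. Every bootstrap step names a median, and the rule that turns the bootstrap into a decision names a mean. This is the only rule given for deciding when the spectra of the groups differ, so the statistic it tests should be beyond doubt.

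Taken literally, the rule either cannot be applied, because the distribution it refers to does not exist, or it lets an analyst claim support in the SAP for either statistic: the median from the steps, the mean from the rule. If that choice were open after the data had been seen, the comparison would lose the protection of pre-specification. The two statistics do not always agree, and spectral power is often skewed, which separates them further.

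**Working it through.** The SAP paragraph gives no sample size, variance or effect size, so there is no figure to reproduce. The check is a comparison of the text, followed by a look at what the word could cost.

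**The sentences in order**

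| Step | Statistic named |
|---|---|
| Summary within each subject | median |
| Summary within each group | median |
| Contrast between groups | median difference |
| 5,000 iterations | distribution of the median difference |
| 99% interval | taken on that same distribution, by back-reference |
| Significance rule | mean difference |

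Five of the six entries agree, and the fifth fixes which interval exists.

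**Could the rule refer to something else?** Three candidates can be tested against the text.

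1. *The mean comparisons in the descriptive part.* These have no frequency axis and come under the general 0.05 level with 95% intervals. The rule requires exclusion of zero over a contiguous frequency range, which makes sense only for the spectra. This candidate fails.
2. *A second, mean-based bootstrap.* The SAP does not say whether the mean would replace the median within subjects, within groups or at both levels. Each choice is a different analysis and none is described. This candidate needs invented steps.
3. *The distribution just built.* It is complete, it has a 99% interval, and it stands in the sentence before. Only the word *mean* does not fit.

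The rule is loosely worded in another place too: it speaks of upper and lower confidence *intervals* where it must mean limits. That supports a slip in drafting rather than a second statistic.

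**How far could the two statistics differ?** This can only be illustrated, with every input assumed: 30 subjects per group, normally distributed log power with between-subject SD 0.5, 30 windows per subject with window log-SD 0.2, one frequency, and a 99% interval for each statistic. The mean version is the difference of group means of the subject medians.

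- Windows resampled only, 1,000 resamples, true log-shifts of 0, 0.2 and 0.4. The two decisions differed in 271/600 = 45%, 126/600 = 21% and 8/600 = 1.3% of comparisons on linear power. On log power they differed in 220/600 = 37%, 120/600 = 20% and 19/600 = 3.2%.
- A separate run with 600 resamples and 150 comparisons per cell shows what lies behind the large rates at zero shift. A 99% interval should exclude zero in about 0.01 × 150 = 1.5 comparisons. With windows only, the median interval did so in 90/150 = 60% (linear) and 91/150 = 61% (log), and the mean interval in 130/150 = 87% and 127/150 = 85%. The decisions differed in 58/150 = 39% and 48/150 = 32%.
- In the same run with subjects resampled as well, the decisions differed in 4/150 = 2.7%, 16/150 = 11% and 48/150 = 32% (linear) and in 4/150 = 2.7%, 20/150 = 13% and 49/150 = 33% (log) at the three shifts.

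The rates at zero shift therefore mostly reflect two intervals that are both far too narrow when only windows are resampled, and the trend across shifts reverses when subjects are resampled too. None of these runs applied the 2 W condition, so none gives a disagreement rate under the SAP's actual rule.

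**The case for a change.** The best case for acting is that a pre-specified decision rule should name the statistic it tests, that this one does not, and that the correction costs one word. The mismatch is in the current text, in two intact adjacent sentences, and no redaction or reading error explains it. The SAP also treats mean and median as distinct in its descriptive part. The illustration supports one element of this case under either resampling scheme: the two statistics can give different decisions, so the word would matter if anyone acted on it.

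That much stands. What does not stand is the step from a wrong word to an open choice. To report a mean difference, an analyst would have to set aside a statistic that the SAP states several times and design a procedure that it does not describe. Anyone holding the SAP could see that departure. The simulated rates do not close this gap. They measure how far two analyses differ, not how likely the second is to be run, and their size depends on assumed inputs and on the resampling scheme. Whether the windows-only scheme is adequate is a separate question that this one word does not touch.

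Reading *mean difference* as a loose term for the difference between groups would explain the slip, though it does not remove it.

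**Conclusion.** The inconsistency is real and clerical. The described procedure produces one between-group distribution, that of the median difference, and one 99% interval, and the significance rule can only be applied to that interval. Reading the rule with *median* in place of *mean* alters no step and no stated number: the 5,000 iterations, the 99% level and the 2 W condition all stay. The expected effect on the results is nil.

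This rests on one assumption, that the analyst carries out the bootstrap as its steps are written. The text supports that strongly, since the steps are complete and the mean reading is not. The word can be tidied if the document is reopened for another reason, but nothing in the analysis depends on it.

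### Descriptive group comparisons name Student's t test although nothing in the SAP makes the groups equal in size or spread; Welch's t test is a cheap safeguard

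*SAP*

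**What the plan says.** The SAP is a single paragraph. Its descriptive part begins "For descriptive statistics, continuous data will be presented using the mean" and SD, or else "the median and its interquartile range, as appropriate". The groups are then compared using Student's "t test for independent samples or Mann-Whitney U test according to their distribution". The paragraph ends: "A significance level of 0.05 with its respective 95% confidence interval will be considered". I read that level as covering the descriptive comparisons as well as the regressions named just before it.

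The SAP mentions neither equal variances, nor a variance check, nor an unequal-variance test. It gives no group sizes. The only step that could balance the groups is matching, and it lies outside the main comparison: "As a sensitivity analysis, we will re-analyze our results after performing a matching by age and a previous cognitive evaluation".

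**The concern.** Student's two-sample t test estimates one common variance from both groups. The larger group dominates that estimate, while the smaller group contributes more to the true variance of the difference in means. If the smaller group is also the more variable one, the standard error is too small and the test rejects too often. If the larger group is the more variable one, the standard error is too large and the test rejects too rarely.

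Groups formed by observed frailty status need not be equal in size, and their characteristics need not be equally variable. The SAP's rule for choosing between the t test and Mann-Whitney does not help. It most naturally refers to shape, so two roughly normal samples with different SDs would still go to Student's test.

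What is at stake is limited to the p-values of the descriptive t tests and any 95% intervals reported with them, which the SAP does not clearly promise. Those p-values could flag differences that are not there or miss differences that are. The Spearman correlations, the bootstrap EEG inference, the regressions and the reported means and SDs are unaffected.

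**Working it through.** **Inputs.** From the SAP: the test (Student's t) and the level (0.05). The SAP states no error rate, power or sample size for this comparison, so there is no planned figure to reproduce. Assumed: two-sided testing, normal data, 80 patients split 40/40, 30/50 or 20/60, and SD ratios from 1 to 2 in either direction.

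**Large-sample formula.** With group sizes n1, n2 and true SDs s1, s2:

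- Pooled variance: P = [(n1 − 1)s1² + (n2 − 1)s2²] / (n1 + n2 − 2)
- Squared standard error that Student's test uses, on average: E = P(1/n1 + 1/n2)
- True squared standard error: V = s1²/n1 + s2²/n2
- Type I error ≈ 2Φ(−1.96 √(E/V))

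At an SD ratio of 1.5:

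- **40 vs 40:** P = (39 × 2.25 + 39)/78 = 1.625; E = 1.625 × 0.05 = 0.08125; V = 2.25/40 + 1/40 = 0.08125. E/V = 1, so 5.0%.
- **30 vs 50, larger SD in the 30:** P = (29 × 2.25 + 49)/78 = 1.4647; E = 1.4647 × 0.05333 = 0.07812; V = 0.075 + 0.020 = 0.095. E/V = 0.822, effective cut-off 1.777, so 7.6%.
- **30 vs 50, larger SD in the 50:** P = 1.7853; E = 0.09521; V = 0.03333 + 0.045 = 0.07833. E/V = 1.215, cut-off 2.161, so 3.1%.
- **20 vs 60, larger SD in the 20:** P = 1.3045; E = 0.08697; V = 0.1125 + 0.01667 = 0.12917. E/V = 0.673, cut-off 1.608, so 10.8%.
- **20 vs 60, larger SD in the 60:** P = 1.9455; E = 0.12970; V = 0.05 + 0.0375 = 0.0875. E/V = 1.482, cut-off 2.386, so 1.7%.

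**Finite-sample values.** These come from numerical integration over the two sample-variance distributions. Each pair is for the larger SD in the smaller group / in the larger group.

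| Split | SD ratio | Student's (%) | Welch's (%) |
|---|---|---|---|
| 40 vs 40 | 1 | 5.00 | 4.99 |
| 40 vs 40 | 1.5 | 5.05 | 5.00 |
| 40 vs 40 | 2 | 5.12 | 5.00 |
| 30 vs 50 | 1 | 5.00 | 5.00 |
| 30 vs 50 | 1.25 | 6.36 / 3.87 | 5.01 / 4.99 |
| 30 vs 50 | 1.5 | 7.55 / 3.15 | 5.01 / 4.99 |
| 30 vs 50 | 2 | 9.35 / 2.36 | 5.01 / 4.99 |
| 20 vs 60 | 1 | 5.00 | 5.03 |
| 20 vs 60 | 1.25 | 7.91 / 2.90 | 5.03 / 5.02 |
| 20 vs 60 | 1.5 | 10.70 / 1.78 | 5.03 / 5.00 |
| 20 vs 60 | 2 | 15.24 / 0.83 | 5.03 / 4.99 |

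A simulation of 1,000,000 datasets at 30 vs 50 and ratio 1.5 gave 7.50% / 3.17% for Student's and 4.97% / 5.01% for Welch's.

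**Does the assumed total matter?** Hardly. At ratio 1.5, Student's gives 7.59% / 3.21% at 15 vs 25 and 7.53% / 3.12% at 60 vs 100. It gives 10.73% / 1.84% at 10 vs 30 and 10.69% / 1.75% at 40 vs 120. The split and the SD ratio drive the result.

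**The case against.** The strongest reply is that the SAP names a valid test, and that the test fails only if sizes and spreads both differ, which the document does not show. Group definitions and recruitment targets usually sit in the protocol, which is not shown here. If it fixes equal groups, Student's test is within about 0.1 points of 5% even at a twofold SD ratio. Every input to the magnitude is an assumption, and the 11% figure needs a 1:3 split with the larger SD in the smaller group. The authors may also have meant any independent-samples t test and left the variance option to the analyst.

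Most of this stands as a limit on severity. No error in the study's own results can be claimed, and the consequence is confined to descriptive p-values. It does not remove the point, because the SAP contains nothing that protects the pooled-variance assumption. The recommendation also does not depend on the unseen group sizes: if they prove equal, switching costs practically nothing. If the authors already intended an unequal-variance test, the change only makes that explicit.

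It is also true that the fix is partial, since Mann-Whitney is sensitive to unequal spread too. In 100,000 simulated normal datasets per setting at ratio 1.5, its type I error was 6.5% / 4.1% at 30 vs 50 and 7.7% / 2.9% at 20 vs 60.

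**Conclusion.** The point holds as a minor improvement. Under the assumed 80 patients and 1.5-fold SD ratio, the descriptive t tests would run at anywhere from about 2% to 11% instead of 5% with unequal groups, and at about 5% with equal groups. Welch's test holds 5% in all these settings. Equal SDs or equal group sizes would each be enough to make the problem negligible, and the SAP does not settle whether either applies. The EEG conclusions do not depend on this choice.

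**What to change.** In the sentence on group comparisons, replace Student's t test for independent samples with *Welch's unequal-variance t test for independent samples* for approximately normal variables. The rest of the sentence can stay. For variables sent to Mann-Whitney, a small p-value should not be read as a difference in medians when the spreads clearly differ.

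The cost is a few words in the SAP and one software option, plus a small loss of power if the SDs are in fact equal. With the effect set so that Student's test has 80.00% power, Welch's has:

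- 79.98% at 40 vs 40
- 79.70% at 30 vs 50
- 78.55% at 20 vs 60
- 79.30% at 15 vs 25
- 76.65% at 10 vs 30, the largest loss examined (80.00 − 76.65 = 3.35 points)
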